6.2 Classification of AEs by Severity and Relationship to Study Drug Administration

- 6.2.1 Adverse Event: Any unfavorable and unintended sign (including an abnormal laboratory finding), symptom or disease temporally associated with the use of a medical treatment or procedure regardless of whether it is considered related to the medical treatment or procedure (attribution of unrelated, unlikely, possible, probable, or definite).
- 6.2.2 Life-threatening Adverse Event: Any AE that places the participant or participant, in view of the Investigator, at immediate risk of death from the reaction.
- 6.2.3 Serious Adverse Event (SAE): Any AE occurring at any dose that results in any of the following outcomes: Death, a life-threatening AE, inpatient hospitalization or prolongation of existing hospitalization, a persistent or significant disability/ incapacity, or a congenital anomaly/birth defect.
- 6.2.4 Please note for hospitalization All hospitalizations (or prolongation of existing hospitalization) for medical events equivalent to CTCAE Grade 3, 4, 5 must be reported regardless of the requirements for Phase of study, expected or unexpected, and attribution. For example, do not report an admission for pharmacokinetic sampling, but do report an admission for a myocardial infarction.
- 6.2.5 Toxicity: Toxicity is a term NOT clearly defined by regulatory organizations. Toxicity has been described as an AE that has an attribution of possibly, probably or definitely related to investigational treatment. To minimize confusion the NCI would recommend that the term toxicity NOT be utilized for AE reporting purposes. The CTCAE continues to use the term 'toxicity' because of familiarity.

- 6.2.6 Unexpected Adverse Event: Any AE that is not listed in available sources including the package insert, the Investigator's Brochure, or the protocol.
- 6.2.7 CTEP Adverse Event Reporting System (CTEP-AERS): An electronic system for expedited submission of AE reports.
- 6.2.8 Attribution: The determination of whether an AE is related to a medical treatment or procedure. Attribution categories:

Definite – The AE is clearly related to the investigational agent.

Probable – The AE is likely related to the investigational agent.

Possible – The AE may be related to the investigational agent.

Unlikely - The AE is doubtfully related to the investigational agent.

Unrelated – The AE is clearly NOT related to the investigational agent.

6.3 Expedited Adverse Event Reporting

6.3.1 Expedited AE reporting for this study must use CTEP-AERS (CTEP Adverse Event Reporting System) accessed via the CTEP home page (http://ctep.cancer.gov). The reporting procedures to be followed are presented in the "CTEP, NCI Guidelines: Adverse Event Reporting Requirements" which can be downloaded from the CTEP home page (http://ctep.cancer.gov). These requirements are briefly outlined in the table below (Section 6.3.3).

A 24-hour notification is to be made to CTEP by telephone at [contact] only when Internet connectivity is disrupted. Once Internet connectivity is restored, a 24-hour notification phoned in must be entered electronically into CTEP-AERS by the original submitter at the site.

- 6.3.2 CTEP-AERS is programmed for automatic electronic distribution of reports to the following individuals: Protocol Chair, Principal Investigator at the local AMC treating institution and AMC Operations and Data Management Center. CTEP-AERS provides a copy feature for other e-mail recipients.
- 6.3.3 Phase 1 and Early Phase 2 Studies: Expedited Reporting Requirements for Adverse Events that Occur on Studies under an IND/IDE within 30 Days of the Last Administration of the Investigational Agent/Intervention^{1, 2}

Note: A death on study requires both routine and expedited reporting regardless of causality, unless as noted below. Attribution to treatment or other cause must be provided.

Death due to progressive disease should be reported as Grade 5 "General disorders and administration site conditions - Disease Progression." Evidence that the death was a manifestation of underlying disease (*e.g.*, radiological changes suggesting tumor growth or progression: clinical deterioration associated with a disease process) should be submitted.

FDA REPORTING REQUIREMENTS FOR SERIOUS ADVERSE EVENTS (21 CFR Part 312)

NOTE: Investigators **MUST** immediately report to the sponsor (NCI) **ANY** Serious Adverse Events, whether or not they are considered related to the investigational agent(s)/intervention (21 CFR 312.64)

An adverse event is considered serious if it results in ANY of the following outcomes:

- 1) Death
- 2) A life-threatening adverse event
- 3) An adverse event that results in inpatient hospitalization or prolongation of existing hospitalization for ≥ 24 hours
- 4) A persistent or significant incapacity or substantial disruption of the ability to conduct normal life functions
- 5) A congenital anomaly/birth defect.
- 6) Important Medical Events (IME) that may not result in death, be life threatening, or require hospitalization may be considered serious when, based upon medical judgment, they may jeopardize the patient or subject and may require medical or surgical intervention to prevent one of the outcomes listed in this definition. (FDA, 21 CFR 312.32; ICH E2A and ICH E6).

ALL SERIOUS adverse events that meet the above criteria MUST be immediately reported to the NCI via CTEP-AERS within the timeframes detailed in the table below.

Hospitalization	Grade 1 and Grade 2 Timeframes	Grade 3-5 Timeframes
Resulting in Hospitalization \geq 24 hrs	10 Calendar Days	24-Hour 5 Calendar
Not resulting in Hospitalization \geq 24 hrs	Not required	Days

NOTE: Protocol specific exceptions to expedited reporting of serious adverse events are found in the Specific Protocol Exceptions to Expedited Reporting (SPEER) portion of the CAEPR.

Expedited AE reporting timelines are defined as:

- "24-Hour; 5 Calendar Days" The AE must initially be reported via CTEP-AERS within 24 hours of learning of the AE, followed by a complete expedited report within 5 calendar days of the initial 24-hour report.
- "10 Calendar Days" A complete expedited report on the AE must be submitted within 10 calendar days of learning of the AE.

¹Serious adverse events that occur more than 30 days after the last administration of investigational agent/intervention and have an attribution of possible, probable, or definite require reporting as follows:

Expedited 24-hour notification followed by complete report within 5 calendar days for:

• All Grade 3, 4, and Grade 5 AEs

Expedited 10 calendar day reports for:

• Grade 2 AEs resulting in hospitalization or prolongation of hospitalization

² For studies using PET or SPECT IND agents, the AE reporting period is limited to 10 radioactive half-lives, rounded UP to the nearest whole day, after the agent/intervention was last administered. Footnote "1" above applies after this reporting period. Effective Date: May 5, 2011

• Expedited AE reporting timelines defined:

- "24 hours; 5 calendar days" The investigator must initially report the AE via CTEP-AERS within 24 hours of learning of the event followed by a complete CTEP-AERS report within 5 calendar days of the initial 24-hour report.
- "10 calendar days" A complete CTEP-AERS report on the AE must be submitted within 10 calendar days of the investigator learning of the event.
- Any medical event equivalent to CTCAE grade 3, 4, or 5 that precipitates hospitalization (or prolongation of existing hospitalization) must be reported regardless of attribution and designation as expected or unexpected with the exception of any events identified as protocol-specific expedited adverse event reporting exclusions.
- Any event that results in persistent or significant disabilities/incapacities, congenital anomalies, or birth defects must be reported via CTEP-AERS if the event occurs following treatment with an agent under a CTEP IND.
- Use the NCI protocol number and the nine-digit AMC participant ID assigned during trial registration on all reports.
- 6.3.4 Clinical Laboratory Results

Clinical laboratory results that are outside of the institution's reference ranges must be reported as adverse events if they are deemed clinically significant by the investigator(s).

- 6.3.4.1 A clinical laboratory abnormality should be deemed clinically significant if any one of the following conditions is met:
 - The laboratory abnormality is not otherwise proved false by a repeat confirmation test.
 - The abnormality suggests a disease and/or organ toxicity that is new or has worsened from baseline.
 - The abnormality is of a degree that requires additional active management, e.g., change of dose, discontinuation of the drug(s), close observation, more frequent follow-up assessments, or further diagnostic investigation.
- 6.3.4.2 In this protocol the following clinical laboratory abnormalities are expected and will not be considered AEs:
 - HIV viral load
 - T Cell subsets
 - LDH

6.4 Routine Adverse Event Reporting

All AEs that require expedited reporting via CTEP-AERS must also be reported in routine study data submissions (Adverse Event Form CRF). Routine reporting of all AEs attributed to therapy (possible, probable or definitely), regardless of grade, should be reported on the Adverse Event Form CRF. Similarly, if participants require radiotherapy, post-treatment AEs related to radiation therapy do not require routine reporting. All Grade 5 events, regardless of attribution to therapy, must be reported in the Adverse Event and Death Forms

in AdvantageEDCSM.

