1.2 Secondary Objectives

- 1.2.1 To evaluate the toxicity of AVD and brentuximab vedotin with HAART.
- 1.2.2 To estimate the partial response (PR) rate, complete response (CR) rate, overall survival (OS), and event free survival (EFS) at 2 and 5 years.
- 1.2.3 To evaluate the effect of AVD and brentuximab vedotin on CD4 and CD8 counts after cycle 1, 4, at the end of therapy, and every 3 months after treatment completion for one year.
- 1.2.4 To investigate the prognostic value of FDG-PET/CT scans at baseline, after cycle 2, and at treatment completion, with respect to 2-year progression free survival.
- 1.2.5 To evaluate HAART status at baseline and to correlate this with tumor response to therapy and OS and PFS.
- 1.2.6 To characterize the histologic subtypes in HIV-HL in the highly active antiretroviral therapy (HAART) era.
- 1.2.7 To assess the neurotoxicity of HAART in combination with AVD and brentuximab vedotin.
- 1.2.8 To evaluate effect of AVD and brentuximab vedotin on viral load after cycles 1, 4, at completion of therapy, and every 3 months after treatment completion for one year.
- 1.2.9 To perform pharmacokinetic and immunogenicity studies to determine drug levels during therapy (See Section 10.0 and Appendix IX).
- 1.2.10 To perform miRNA profile analysis on the HIV-HL tumor specimens and to correlate miRNA expression with OS, PFS, tumor response to therapy, histologic subtype of HIV-HL, and HIV disease characteristics (See Section 10.0 and Appendix VIII).
- 1.2.11 To perform tissue microarray analysis on HIV-HL tumor specimens and to correlate the markers studied with OS, PFS, and tumor response to therapy (See Section 10.0 and Appendix VIII).
- 1.2.12 To identify EBV associated tumor derived DNA in the plasma of study participants, and to correlate these levels during therapy with disease response and OS (See Section 10.0 and Appendix XI). This objective will only be performed in the Phase II portion of the study.

- 1.2.13 To identify cytokines in the plasma of participants during therapy that can be used as tumor and prognostic markers. (See Section 10.0 and Appendix X). This objective will be done only in the Phase II portion of the study.
- 1.2.14 To assess latent and expressed HIV reservoirs before, during, and post chemotherapy. To understand how cytotoxic chemotherapeutic agents affect HIV expression (See Section 10.0 and Appendix XII).

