4.7 Criteria for Early Study Termination

- 4.7.1 An early stopping rule will be established such that the trial will be terminated if either or both of the following conditions hold:
 - 1. If the highest dose, the 1.2mg/kg dose, moves forward into the phase II portion of the study, and if more than 10% of the participants experience a grade 3 motor or sensory neurotoxicity lasting for more than 4 weeks, the trial will be terminated. The first 10 participants in the phase II portion of the study at the 1.2 mg/kg dose will be monitored for this outcome. If more than 3 out of the 10 participants experience grade 3 neurotoxicity, this will be considered sufficient to stop the trial. With an underlying probability of grade 3 neuropathy of no more than 10%, the probability of observing > 3 participants with grade 3 neuropathy is less than 5%.
 - 2. If any PML case is diagnosed when the CD4 count is above 50, the trial will be terminated.

4.7.2 Request by the protocol chairs, AMC, IRB, NCI, OHRP, or pharmaceutical sponsors.

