6.4.1 Timeline for routine adverse event reporting

All adverse events will be assessed by the investigator in the study source from the first dose of protocol therapy through the post-treatment discontinuation visit (one month if discontinuing treatment early; 6-8 weeks at scheduled protocol therapy completion). After this evaluation, assessment and reporting of AEs will only be required for all grade 5 AEs and any SAE that the investigator considers related to AMC-085 protocol therapy.

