11.4 Analysis of Secondary Endpoints

Descriptive summaries and exploratory analyses for secondary objectives will be conducted. Significance for comparisons will be at the p<0.05 level.

Secondary objectives include:

1. To evaluate toxicity of AVD and brentuximab vedotin with HAART.

- 2. To estimate the partial response rate, complete response rate, overall survival (OS), event free survival at 2 and 5 years. To evaluate effect of AVD and brentuximab vedotin on CD4 and CD8 counts after 2 cycles, 6 cycles, and every 3 months after treatment completion for one year.
- 3. To evaluate effect of AVD and brentuximab vedotin on viral load after 2 cycles, 6 cycles, and every 3 months after treatment completion for one year
- 4. To investigate the prognostic value of FDG-PET scans at baseline and after 2 cycles in participant with HIV and HL with respect to 2 year progression free survival.
- 5. To evaluate HAART status at baseline for difference in outcome.
- 6. The characterization of histologic subtypes in HIV-HL in the HAART era.
- 7. To assess additional neurotoxicity in combination with HAART and AVD and brentuximab vedotin.

The frequency of AEs and their severity will be tabulated to evaluate tolerance of AVD and brentuximab vedotin with HAART. Further, binomial probabilities and their 95% confidence intervals will be used to estimate the response rates (i.e., partial response rate, complete response rate, overall response rate) and event free survival at 2 and 5 years of AVD and brentuximab vedotin for a treatment of participants with stage III/IV HIV-associated Hodgkin Lymphoma.

Repeated measures analysis of variance (ANOVA) models will be used to evaluate the effect of AVD and brentuximab vedotin on CD4 counts, CD8 counts and viral load after 1, 4, and 6 cycles, and every 3 months after treatment completion for one year.

Log-rank analysis will be used to investigate the prognostic value of FDG-PET scans at baseline, after 2 cycles and post-therapy in participants with HIV and HL with respect to progression free survival.

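### Adverse events reach the AE form through a site-attribution filter, so non-serious neuropathy blamed on HAART or HIV can be missing from the HAART-combination toxicity and neurotoxicity results

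*Combined protocol and SAP*

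**What the plan says.** **What goes on the AE form.** AMC section 6.4 gives three routes. The first is attribution: "Routine reporting of all AEs attributed to therapy (possible, probable or definitely), regardless of grade, should be reported on the Adverse Event Form CRF". The second is any event that needs expedited reporting. The third is death: "All Grade 5 events, regardless of attribution to therapy, must be reported in the Adverse Event and Death Forms". French section 14.4 has the same text.

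**What happens to the rest.** Under AMC section 6.4.1, "All adverse events will be assessed by the investigator in the study source from the first dose of protocol therapy" up to the post-treatment discontinuation visit. An event outside the three routes therefore stays in site records. The French protocol has no counterpart to 6.4.1; its schedule of evaluations shows only continuous AE reporting.

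**What attribution means.** Section 6.2.8 defines every category against the investigational agent. HAART is not a category.

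**What the data are for.** Objective 1.2.7 is "To assess the neurotoxicity of HAART in combination with AVD and brentuximab vedotin", and objective 1.2.1 asks about toxicity with HAART. Section 11.4 (French 16.4) plans: "The frequency of AEs and their severity will be tabulated to evaluate tolerance of AVD and brentuximab vedotin with HAART". It also tabulates neurotoxicity frequency, without naming the data source.

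**The stopping rule.** Section 4.7.1 (French 13.4) terminates the trial "if more than 10% of the participants experience a grade 3 motor or sensory neurotoxicity lasting for more than 4 weeks", monitored in the first 10 phase II participants with a trigger of more than 3 of 10. No attribution condition is written.

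**The concern.** The objectives concern a combination, but the collection rule asks whether the site links the event to protocol therapy. HAART is compulsory (sections 3.1.16 and 4.4.2), there is no control arm, and treatment is open-label. A site cannot reliably separate HAART, HIV, vinblastine and brentuximab vedotin as causes of neuropathy, yet its judgment decides what is tabulated.

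The protocol itself supplies reasons to look elsewhere for a cause. Section 2.4.5 links neuropathy during ABVD to ritonavir-based HAART and says that many HAART drugs still affect CYP450 enzymes. Section 3.2.5 excludes only grade 2 or greater neuropathy, so participants may enter with grade 1. What is at stake is a downward bias in the reported neuropathy rates, which are the subject of objective 1.2.7.

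**Working it through.** **Step 1. Trace each kind of neuropathy to the form** (AMC sections 6.1, 6.3.3, 6.4 and 6.4.1).

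| Neuropathy during the reporting period | At least possibly related | Unlikely or unrelated |
|---|---|---|
| Grade 1-2, non-serious | Entered | No required route |
| Grade 3-4, serious | Entered | Entered through expedited reporting |
| Grade 3-4, read as non-serious | Entered | Depends on how 6.3.3 is read |

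The second row rests on two provisions. Section 6.3.3 makes serious events reportable whether or not they are related. The exemption list in section 6.1 covers sensory and motor neuropathy only up to grade 2, so grade 3 is not exempt.

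The third row is ambiguous. The timeframe table in 6.3.3 covers grades 3-5 with or without hospitalization, but its lead-in confines it to serious events: "adverse events that meet the above criteria MUST be immediately reported to the NCI via CTEP-AERS within the timeframes detailed in the table below". The clear gap is the first row, last column.

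**Step 2. Direction of the bias.** Let p be the true proportion with neuropathy and f the share of those participants whose only neuropathy falls in that gap. The recorded proportion is p × (1 − f). Since f cannot be negative, the rate is understated or unchanged, never overstated.

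**Step 3. Size.** The documents give no value for f. The only conversion available uses the planned 51 phase II participants: each one missed lowers the observed incidence by 1/51 = 0.0196, about 2.0 percentage points. The number missed is unknown and could be zero.

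**Step 4. The stopping count.** First, the plan's own figure. With n = 10 and a true grade 3 rate of 0.10,

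P(X > 3) = 1 − Σ C(10,x) 0.1^x 0.9^(10−x), x = 0 to 3
= 1 − (0.3487 + 0.3874 + 0.1937 + 0.0574) = 0.0128,

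which agrees with the stated figure of less than 5%. That calculation presumes that every grade 3 event is counted. By Step 1, a grade 3 event goes uncounted only if it is judged both non-serious and not even possibly related, or if it arises late. More than 30 days after the last dose, 6.3.3 expedites a serious event only if it is attributed; after the post-treatment visit, 6.4.1 asks only for grade 5 events and related serious events. The rule's event is also one that lasts more than 4 weeks, and 6.3.3 counts a substantial disruption of normal life functions as serious. No loss rate for such events can be taken from the documents.

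**The case against.** **Possible is a low bar.** Section 6.1 lists sensory neuropathy as likely (over 20%) with brentuximab vedotin, section 7.1.2 gives 10% peripheral neuropathy for vinblastine, and section 2.4.5 names the overlap. A HAART-chemotherapy interaction is by its nature possibly related to chemotherapy, and ritonavir is now prohibited. This stands as a limit on size: many sites will tick possible. It does not close the gap, because the rule still permits omission.

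**Neuropathy is collected elsewhere.** The FACT/GOG questionnaire is completed at the start of each cycle without attribution (section 8.2.4). That is true, but it carries no CTCAE grade, and section 11.4 gives it no analysis. It cannot supply AE frequency by severity.

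**Toxicity means related events.** Section 6.2.5 describes the term that way. The same paragraph advises against using it for AE reporting, however, and section 11.4 speaks of AEs.

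**Therapy might include HAART.** Section 6.4 does not define the word. If HAART were included, HAART-attributed events would be captured. Section 6.2.8, and the reference in 6.4.1 to AMC-085 protocol therapy, point the other way.

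**A stronger reading to avoid.** A reader might infer that the neurotoxicity safeguard is materially weakened, and might put a number on it by assuming that a fixed share of grade 3 events is lost. The documents do not support this. Such a share would be invented, and it is implausible for persistent grade 3 neuropathy given Step 4. Dose delays and reductions for grade 2-3 neuropathy carry no attribution condition (Table 5-A), and the monthly calls in section 6.0 cover all AEs encountered, so other routes also bring such events to notice.

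**Conclusion.** The point holds for the HAART-combination objectives. Non-serious neuropathy, mainly grade 1-2, that a site judges unlikely or unrelated has no required route to the AE form, so the tabulated rates can be biased downward. This rests on reading therapy in sections 6.4 and 14.4 as excluding HAART, and on the neurotoxicity tabulation drawing on the AE form, as its neighbouring AE tabulation appears to. The direction is certain; the size is not derivable and may be modest.

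It would go too far to say that neuropathy blamed on HAART is left out as a rule, since a possible relationship is enough for entry. For the stopping count, omission remains a narrow possibility with no supportable magnitude. The change is worth making because it is cheap and the affected event is named in an objective.

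**What to change.** - **AMC 6.4 and French 14.4:** from first dose to the treatment discontinuation visit, require entry on the AE form of all peripheral motor and sensory neuropathy of any grade, and of all grade 3-5 AEs, whatever the attribution.
- **AMC 11.4 and French 16.4:** tabulate all-cause frequencies for neuropathy and for grade 3-5 AEs, with attributed events in a second column. Label lower-grade AEs other than neuropathy as attributed only. Name the data source for the neurotoxicity tabulation, with FACT/GOG as a supporting summary.
- **AMC 4.7.1 and French 13.4:** state that the count uses grade 3 events whatever the attribution. The threshold does not change.

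The cost is wording, modest extra data entry and slightly higher reported rates. AMC sites already assess these events in source under 6.4.1; the French protocol should say the same. If the change comes mid-trial, earlier participants need back-entry from source, or the report must say that their all-cause data are incomplete. This is a live question: the French protocol is dated April 2019, while its last inclusion was anticipated for June 2017.
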